APPENDIX 4. OLE SCHEDULE OF ASSESSMENTS

	Q2 WEEKS (± 3 days)	Q12 weeks (± 3 days)	Q 24 weeks (± 3 days)	Q52 Weeks (± 3 days)/EOT	Final Safety Follow- up Visit 4 Weeks (± 3 days) after Last treatment EOS/ET	Final Safety phone call 60 Days (+3 days) after last treatment
Informed Consent & Assent/Eligibility ^a						
Vital Signs ^b	x	x	x	x	x	
Chemistry & Hematology (Central lab)			x		x	
PFTs / Height (ulna length) ^c			x	x ^h	x ^c	
Muscle Function Tests ^d		x	x	x ^h	x ^c	
Physical Examination ^e			x		x	
Cardiac MRI				x		
Weight/Weight Based Dose Adjustment ^f		x	x			
Specialty Labs (PK, HAHA, and HAHA-NA) ⁱ			x		x	
Pamrevlumab Infusion	x	x	x	x		
AEs / SAEs	x	x	x	x	x	x
Concomitant Medications	x	x	x	x	x	x

Abbreviations: AE = adverse event; EOS = End of Study; EOT = End of Treatment; ET= Early Termination; PFTs = Pulmonary Function Test

- a.) Prior to starting infusions and procedures for the OLE, subject must sign the OLE consent and be confirmed eligible at the Week 52 visit of the main study.
- b.) Vital signs (pulse, respiration, sitting BP, temperature) to be collected at every infusion visit: within 30 minutes pre-infusion, and within 30 minutes after completion of infusion. For EOS/ET, vitals to be completed one time only.

- c) MFTs and PFTs do not need to be done at the final Safety follow-up visit, ONLY during an ET visit and ONLY if the last test was not conducted within 8 weeks of the visit.
- d.) Muscle Function Tests (MFTs): Performance of Upper Limb (v. 2.0), and Grip Test.
- e.) Pulmonary Function Tests (PFTs) include forced vital capacity, forced expiratory volume in 1 second, and peak expiratory flow rate to be performed. Height should be measured at each PFT interval using ulna length to approximate standing height.
- f.) Weight will be measured every 12 weeks to determine dose for the subsequent 12-week interval. Weight is collected during the dose adjustment visit or can be done up to two weeks in advance.
- g.) Full physical exam including chest auscultation is completed per the institution's local practice (i.e., every 24 weeks)
- h.) MFTs and PFTs only to be done at the end of treatment visit (last infusion visit), otherwise, they are done every 12 or 24 weeks, respectively
- i.) PK, HAHA and HAHA-NA sampling required at all blood draw visits in the OLE. PK is not optional in the OLE. See [Appendix 2](#) for more detail of blood draws including sample required for immunogenic reaction.

Signature Page for VV-CLIN-013263 v1.0

**CHANGE HISTORY**

Version	Date	Description
1.0	23May2023	Final approved version

**LIST OF ABBREVIATIONS**

Abbreviation	Definition
ADaM	Analysis Data Model
AE	Adverse Event
ALT	Alanine Aminotransferase
ANCOVA	Analysis of Covariance
AST	Aspartate Aminotransferase
ATC	Anatomical Therapeutic Chemical
BMI	Body Mass Index
BP	Blood Pressure
BPM	Beats Per Minute
BSA	Body Surface Area
BTR	Best-Test Read
CBC	Complete Blood Count
CDE	Center for Drug Evaluation (China)
CRF	Case Report Form
CS	Clinically Significant
CSR	Clinical Study Report
CTCAE	Common Terminology Criteria for Adverse Events
DBL	Database Lock
DCM	Dilated Cardiomyopathy
DMD	Duchenne Muscular Dystrophy
DMC	Data Monitoring Committee
ECG	Electrocardiogram
EE	Efficacy Evaluable
EoS	End of Study
EoT	End of Treatment
FEV 1	Forced Expiratory Volume in 1 Second
FG-3019	FibroGen-3019 (Recombinant Human Monoclonal Antibody), Pamrevlumab
FVC	Forced Vital Capacity
GCS	Global Circumferential Strain
HAHA	Human Anti-Human Antibody

Abbreviation	Definition
HHM	Handheld Myometry
ICF	Informed Consent Form
IP	Investigational Product
ITT	Intent-to-Treat
IV	Intravenous
kg	Kilogram
LGE	Late Gadolinium Enhancement
LLN	Lower Limit of Normal
LTFU	Lost to Follow-up
LVEF	Ventricular Ejection Fraction
MedDRA	Medical Dictionary for Regulatory Activities
mg	Milligram
MMRM	Mixed Model Repeated Measures
MRI	Magnetic Resonance Imaging
NCI	National Cancer Institute
NCS	Not Clinically Significant
OLE	Open Label Extension
PD	Pharmacodynamics
PEF	Peak Expiratory Flow
PFT	Pulmonary Function Test
PK	Pharmacokinetic
ppFVC	percent predicted FVC
PRO	Patient Reported Outcome
PT	Preferred Term
PTT	Partial Prothrombin Time
PUL	Performance of Upper Limb
QoL	Quality of Life
ROM	Range of Motion
RCM	Random Coefficient Model
SAF	Safety Analysis Set
SAE	Serious Adverse Event

Abbreviation	Definition
SAP	Statistical Analysis Plan
SD	Standard Deviation
SDTM	Study Data Tabulation Model
SE	Standard Error
SoA	Schedule of Assessments
SOC	System Organ Class
TEAE	Treatment Emergent Adverse Event
TESAE	Treatment Emergent Serous Adverse Event
TFLs	Tables, Figures and Listings
ULN	Upper Limit of Normal
WHODD	World Health Organization Drug Dictionary

## 1. INTRODUCTION

This statistical analysis plan (SAP) provides a more technical and detailed elaboration of the statistical analyses of study data as specified in the Study Protocol FGCL-3019-093 Amendment 6, 01 November 2022. Specifications of tables, figures, and listings (TFL) are contained in a separate document. The statistical analyses and summary tabulations described in this SAP will provide the basis for the results sections of the clinical study report (CSR) for this study. The SAP will be finalized and signed off prior to database lock (DBL). Any major modification of this SAP after the signoff will be documented in an SAP amendment or the CSR.

This SAP is only for the main study period. The Open Label Extension (OLE) will have a separate SAP. A population PK analysis, as well as an exposure-response analysis, will be defined in a separate PK analysis plan.

Based on regional regulatory filing needs, regional specific population will be analyzed following this same SAP. Refer to [Appendix 6](#) if regulatory submission in China is pursued.

## 2. STUDY OBJECTIVES

The overall objective of this trial is to evaluate the efficacy and safety of pamrevlumab versus placebo in combination with systemic corticosteroids in subjects with non-ambulatory Duchenne Muscular Dystrophy (DMD) (age 12 years and older).

## 3. STUDY DESIGN

### 3.1. Overview

Study FGCL-3019-093 is a Phase 3, global, randomized, double-blind, placebo-controlled multi-center study. The goals of the study are to evaluate the efficacy and safety of pamrevlumab compared to placebo in subjects with non-ambulatory Duchenne Muscular Dystrophy over a 52-week period.

### 3.2. Study Population

Approximately 92 male subjects will be enrolled in this trial, globally.

### 3.3. Sample Size Determination

This section is updated based on latest publications and the study enrollment.

This study is planned to enroll a total of approximately 92 subjects with a 1:1 randomization ratio of assigning to pamrevlumab or placebo, respectively. With Performance of Upper Limb (PUL) version 2.0, the sample size of 92 subjects is needed to detect a treatment difference of 2.0 between treatment arms in change from baseline in the total score of PUL at Week 52, assuming a standard deviation of 2.9 with a 90% power, based on a two-sided two-sample t-test at the alpha level of 0.05. A sample size of 82 subjects will provide the study with at least 85% power to detect the same assumed treatment difference.

### 3.4. Randomization and Treatment Assignment

Subjects will be randomized with a 1:1 ratio to one of the two study treatment arms as follows:

- Arm A: pamrevlumab 35 mg/kg IV infusion Q2 weeks + systemic deflazacort or equivalent potency of corticosteroids administered orally.
- Arm B: matching placebo IV infusion Q2 weeks + systemic deflazacort or equivalent potency of corticosteroids administered orally.

### 3.5. Study Periods

This study consists of the following study periods (Figure 1):

- Main (double-blind, placebo-controlled) study period:
  - Screening period: Up to 4 weeks
  - Treatment period: 52 weeks
- Optional, open label extension (OLE) period:

[figure not shown]
Subjects who complete week 52 of the main study period (regardless of the number of study drug infusions received) will be eligible to participate in the open-label extension (OLE) where all subjects will be treated with pamrevlumab. If a subject discontinues the main study period early for any reason, they will not be eligible for inclusion in the OLE.

- Follow-up period/final safety assessment:
  - 28 days after last dose: scheduled visit
  - 60 days after last dose: follow-up phone call, for a final safety assessment

Subjects who discontinue study treatment for any reason should be encouraged to return to the investigative site to complete final safety and efficacy assessments.

A schematic overview of the study is provided in Figure 1.

**Figure 1: FGCL-3019-093 Study Schema**

Abbreviations: EOS= End of Study, ET=Early Termination

a) Subjects who discontinue the study early, for any reason, will complete an early termination visit 28 days (+/- 3 Days) and a final safety follow-up phone call 60 days (+ 3 days) after the last infusion.

### 3.6. Study Assessments

The intent of this study is to evaluate the efficacy and safety profile of pamrevlumab in combination with systemic corticosteroids in subjects with non-ambulatory Duchenne muscular dystrophy (age 12 years and older).

The following assessments will be assessed by the schedules defined in the protocol (Schedule of Assessments (SoA) in the Appendix of the protocol):

- Performance of Upper Limb (PUL) V2.0
- Pulmonary Function Test (PFT) including
  - Forced Vital Capacity (FVC)
  - Peak Expiratory Flow (PEF)
  - Forced Expiratory Volume in 1 second (FEV1)
- Grip strength of the hands by Handheld Myometry (HHM)
- Left Ventricular Ejection Fraction percentage (LVEF %), assessed by magnetic resonance imaging (MRI)
- Duchenne Video Assessment (DVA)
- Dilated Cardiomyopathy (DCM) by genetic analysis
- Fibrosis score of the biceps brachii, assessed by MRI
- Cardiac fibrosis score, assessed by Late Gadolinium Enhancement (LGE)
- Myocardial Circumferential Strain [Global Circumferential Strain (GCS)], assessed by cardiac MRI

Safety assessments will be assessed throughout the study and in accordance with the SoA in the protocol, including but not limited to, adverse events (AEs), concomitant medications, laboratory tests, vital signs, physical exams, etc.

The following assessments will be assessed centrally by independent external vendors or study committees: PFTs, MRI, PUL V2.0. and DVA.

In addition, an independent Data Monitoring Committee (DMC) will review safety and other clinical data (with the authority to unblind such data as needed) on a periodic basis to monitor overall subject safety.

## **4. STUDY ENDPOINTS**

### **4.1. Primary Endpoint**

#### **4.1.1. Function assessment:**

- Change in the total score of Performance of Upper Limb [(PUL) version 2.0], from baseline to Week 52

### **4.2. Secondary Endpoints**

- Change in percent predicted forced vital capacity (ppFVC) from baseline to Week 52, assessed by spirometry
- Change in the total score of Mid-level of PUL from baseline to Week 52
- Change in the Grip strength of the hands from baseline to Week 52, assessed by Handheld Myometry (HHM)
- Change in Left Ventricular Ejection Fraction percentage (LVEF %) from baseline to Week 52, assessed by MRI
- **Composite of endpoints**  
Mean observed z score for each of the 3 composite endpoints (PUL, ppFVC), (PUL, ppFVC, Grip Strength), (PUL, ppFVC, Grip Strength, LVEF%).

### **4.3. Safety Assessments**

- All treatment emergent adverse events (TEAEs), treatment emergent serious adverse events (TESAEs), clinically significant laboratory test abnormalities, discontinuation of treatment due to treatment-related AEs, hypersensitivity/anaphylactic reactions, and infusion reactions
- Number and percentage of subjects with hospitalizations due to any serious adverse events with pulmonary and/or cardiac cause(s)
- Number and percentage of subjects with bone fractures
- Ulna length measurements for indirect measure of growth velocity (cm/year) for subjects under the age of 18

### **4.4. Exploratory Endpoints**

- Change in the subscores of the regional dimensions (High-level (Shoulder), Distal-level (Wrist and Hand)) of PUL, from baseline to Week 52
- Change in Duchenne Video Assessment (DVA) severity percentage from baseline to Week 52
- Change in percent predicted Forced Expiratory Volume at 1 second (ppFEV1) from baseline to Week 52

- Change in percent predicted peak expiratory flow (ppPEF) from baseline to Week 52, assessed by spirometry
- Progression of Dilated Cardiomyopathy (DCM) by genetic analysis at Week 52

**Fibrosis/MRI assessments:**

- Changes in fibrosis score of the biceps brachii, from baseline to Week 52, assessed by MRI
- Changes in cardiac fibrosis score from baseline to Week 52, assessed by Late Gadolinium Enhancement (LGE)
- Change in Myocardial Circumferential Strain [Global Circumferential Strain (GCS)] percentage from baseline to Week 52, assessed by cardiac MRI

#### **4.5. Pharmacokinetics/pharmacodynamics (PK/PD) assessment**

- Population PK/PD analysis

### **5. GENERAL STATISTICAL CONSIDERATIONS**

#### **5.1. General Conventions**

All analyses will be performed using SAS® Version 9.4 or higher. All data collected will be presented by data listings for review and substantiation of summary tables.

##### **5.1.1. Analysis for Categorical Endpoints**

Frequency distributions (number and percentage of subjects) will be presented for categorical variables.

For categorical variables, the confidence interval of proportions for each treatment group will be calculated using the Clopper-Pearson method as appropriate. Bar graphs of proportions for categorical variables will be plotted as appropriate.

##### **5.1.2. Analysis for Continuous Endpoints**

For continuous variables, descriptive statistics, including n, mean, standard deviation (SD), median, minimum, and maximum, will be presented. Unless otherwise stated, all confidence intervals will be two-sided 95% confidence intervals.

For selected continuous variables, line graphs of group mean (and standard error (SE)) and mean change from baseline (and SE) values will be plotted over visits.

Baseline characteristics, safety, efficacy, and other data will be summarized by treatment arm based on available data in the mITT/ITT or Safety Analysis Set, except for the parameters specifically indicated otherwise.

Efficacy and safety analyses for treatment comparisons will be based on data observed during the main study period (52 weeks).

The statistical comparisons will be done between treatment groups as deemed appropriate. The treatment groups will be presented as follows:

- Pamrevlumab
- Placebo

## **5.2. Analysis Sets**

The following analysis sets will be used for statistical analysis:

### **5.2.1. Intent-to-Treat Set (ITT)**

The ITT set will include all randomized subjects. Subjects will be analyzed according to their randomized treatment arm.

### **5.2.2. Modified ITT Population (mITT)**

The mITT population enriched for expected change will include subjects from the ITT set with a PUL Entry score  $\geq 2$  (excluding PUL entry scores of 1) at baseline.

### **5.2.3. Per-Protocol Set (PPS)**

The per-protocol set will be defined as all randomized subjects who completed at least 24 doses of treatment, with baseline and at least one post-baseline PUL assessments, did not early terminated from treatment or study, and no major protocol deviation(s) that significantly impact efficacy analyses.

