### 6.6. Efficacy Analyses

The primary and secondary endpoints will be tested using a fixed sequence procedure to preserve the study-wide error rate of 5%. Under the sequential analysis, the primary and secondary efficacy endpoints will be tested in a predefined sequence according to the order listed in Table 1 each at the usual alpha= 0.05 level of statistical significance. The testing will cease when a failure occurs in the pre-determined sequential hypothesis testing and all p-values for the subsequent testing will be considered nominal.

All analyses for efficacy endpoints will be performed for the mITT during the On-Study period (Section 5.3.1.1), unless noted otherwise. Sensitivity analysis on ITT will also be performed on primary and secondary endpoints as supportive evidence.

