**PUL 2.0 scale:**

- The PUL 2.0 scale, with maximum total score = 42

- High Level: Shoulder Dimension, 6 items: Max score = 12
- Mid-level: Elbow Dimension, 9 items: Max score = 17
- Distal level: Wrist and Hand Dimension, 7 items: Max score = 13

Only 1 item in each domain is allowed missing. The score of the missing item will be imputed by the mean of the non-missing items in the domain. If the total score of any domain is missing (the high-level domain only applies to subjects with Item A score  $\geq 3$ ), then the total score will be missing. The total score of PUL is the sum of the total scores of the three domains (if Item A score  $\geq 3$ ) or two domains (Mid-level and Distal level, if Item A score  $< 3$ ).

The last measurement prior to first dose of study drug from Muscle Function Tests (MFTs) at Day 1 will be used to establish baseline.

The primary efficacy endpoint will be analyzed using mITT as the primary analysis set.

The hypothesis to be tested for the primary efficacy analysis is:

**H0:** Change from Baseline in the total score of PUL at Week 52 for the pamrevlumab arm = Change from Baseline in the total score of PUL at Week 52 for the placebo group

Versus:

**H1:** Change from Baseline in the total score of PUL at Week 52 for the pamrevlumab arm  $\neq$  Change from Baseline in the total score of PUL at Week 52 for the placebo group

H0 will be tested at the two-sided alpha = 0.05 level of significance and will be rejected if the p < 0.05 from the test.

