##### **6.6.1.2.7.2. Population of Interest**

PPS as defined in [Section 5.2.3](#).

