## 7. CHANGES FROM PROTOCOL

- **Changes for the primary analysis:**

The mITT population is defined in [Section 5.2.2](#) and is used for the analysis of primary and secondary efficacy endpoints. In addition, sensitivity analyses will be conducted for the primary and secondary efficacy endpoints in the ITT population.

- **Rationale for the changes:**

- Recently published observational data suggest that patients with PUL 2.0 entry score 1 have minimal PUL 2.0 changes over a one-year treatment period [19]. Consequently, there is no meaningful opportunity to demonstrate the benefit of a therapeutic drug in the PUL 2.0 entry score 1 subpopulation. This information was published in April, 2023, after the study was already designed.
- This is the largest observational study of PUL 2.0 scores to date in 311 patients followed longitudinally over 24 months with 808 paired assessments [19]. In this study, the decline of PUL 2.0 scores for patients with a PUL 2.0 entry score of 1 was very low at 12 and 24 months compared to patients with higher PUL 2.0 entry scores. For example:
  - At 12 months, the mean PUL 2.0 total score change on all the paired assessments for patients with PUL 2.0 entry scores of 1 was -0.84 compared to -2.05 for PUL 2.0 entry score of 3. Changes were even greater for patients with PUL entry scores of 4, 5, or 6.
  - At 24 months, the mean PUL 2.0 total score change on all the paired assessment for patients with PUL 2.0 entry scores of 1 was -1.78 compared to -3.82 for patients with PUL 2.0 entry score of 3. Changes were even greater for patients with PUL 2.0 entry scores of 4, 5, or 6.
- Based on these results, the authors concluded that differences in PUL 2.0 entry scores should be taken into account when designing and analyzing clinical studies [19] and this supports the proposed change to the analysis population to exclude patients with a PUL baseline score of 1.
- Based on these results, the authors concluded that differences in PUL 2.0 entry scores should be taken into account when designing and analyzing clinical studies [19].
- In an early study by Pane from a cohort of 187 patients with DMD, which included 90 non-ambulatory patients, patients with the lowest PUL entry scores of 0 or 1 had minimal further progression during a 12-month follow-up period.

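### The per-protocol set is built on all randomised subjects but the primary analysis uses the mITT, so a gap between the two results cannot be put down to adherence alone

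*SAP*

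**What the plan says.** **Primary set.** Under the PUL 2.0 scale heading in SAP 6.6.1: "The primary efficacy endpoint will be analyzed using mITT as the primary analysis set". SAP 5.2.2 describes that set: "The mITT population enriched for expected change will include subjects from the ITT set" with an entry score of at least 2 at baseline, that is, "excluding PUL entry scores of 1".

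**Default.** SAP 6.6 says: "All analyses for efficacy endpoints will be performed for the mITT during the On-Study period", unless another population is noted.

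**Per-protocol set.** SAP 5.2.3 reads: "The per-protocol set will be defined as all randomized subjects who completed at least 24 doses of treatment". It also requires a baseline and at least one later PUL assessment, no early termination of treatment or study, and no major deviation that bears on efficacy. Entry score is not mentioned. SAP 6.2 adds only that major deviations lead to exclusion from this set.

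**Per-protocol analysis.** SAP 6.6.1.2.7.2 gives the population as "PPS as defined in" Section 5.2.3. That notes another population, so the mITT default does not apply. The estimand strategy, intercurrent-event handling and analysis variable are those of the primary analysis. The model is also the primary one if linearity holds.

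**Why score 1 was removed.** SAP 7 says "there is no meaningful opportunity to demonstrate the benefit of a therapeutic drug in the PUL 2.0 entry score 1 subpopulation". It cites 12-month natural-history changes in which the mean for "patients with PUL 2.0 entry scores of 1 was -0.84 compared to -2.05 for PUL 2.0 entry score of 3".

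**The concern.** A per-protocol analysis helps a reader of the primary result when it changes one thing: who received and completed treatment as planned. Here it changes two. Even if every subject met the dose, assessment, completion and deviation criteria, the per-protocol set would not equal the primary set, because the entry-score-1 subjects would be back in it.

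The model does not separate the two changes. In the SAP's sample code for the primary model, entry score is a main effect and there is no treatment-by-entry-score term. If the effect is smaller in score-1 subjects, it is averaged into the per-protocol estimate.

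What is at stake is interpretation. A per-protocol estimate below the primary one could be read as fragility when it reflects population mix. Conversely, the mix could hide a real difference among adherent subjects.

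The SAP gives no reason for the departure. The MMRM, MI ANCOVA, jump-to-control, tipping-point, on-treatment and cumulative-loss analyses all point back to the mITT. The ITT analysis departs from it by name, and SAP 7 mentions that. Protocol 8.2 defines no per-protocol set, and SAP 7 does not mention one.

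**Working it through.** **Inputs.**
- Treatment difference 2.0, SD 2.9, two-sided alpha 0.05, 1:1 allocation (SAP 3.3).
- About 15 subjects removed, 97 dosed, 82 in the mITT, 87% power (SAP 7).
- Natural-history change of -0.84 at 12 months for entry score 1 (SAP 7).

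**1. The plan's own figures.** The two-sample t-test needs 46 per arm (92 in total) for 90% power; power there is 90.5%. With 41 per arm (82 in total) it is 87.0%. Both stated figures are reproduced. The normal approximation used below gives 87.8% at 82.

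**2. Share of score-1 subjects.** 15/97 = 15.5%, if everyone dosed qualified or both groups qualified at the same rate.

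**3. Expected difference in a mixed set.** Let m be the subjects with entry score 2 or more, k those with entry score 1, and e the assumed effect in the latter. The approximate average effect is (m × 2.0 + k × e)/(m + k).
- e = 0: (82 × 2.0 + 15 × 0)/97 = 164/97 = 1.69, which is 15% below 2.0.
- e = 0.84 (whole natural-history decline halted): (164 + 12.6)/97 = 176.6/97 = 1.82, which is 9% below 2.0.
- e = 2.0: the average stays at 2.0 and there is no dilution.

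**4. Power.** This is Φ(d/(SD × √(2/n)) − 1.96), with n per arm.
- mITT only, n = 41: 2.0/(2.9 × √(2/41)) = 3.12, power 87.8%.
- All 97, e = 0, n = 48.5: 1.69/(2.9 × √(2/48.5)) = 2.87, power 81.9%.
- All 97, e = 0.84: 1.82/0.589 = 3.09, power 87.1%.
- All 97, e = 2.0: power 92.5%, because the set is larger.

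**5. Unequal qualification, e = 0.** Take 70 mITT subjects in the per-protocol set; power without score-1 subjects is 82.3%.

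| Score-1 subjects added | Difference | Power |
|---|---|---|
| 5 | 140/75 = 1.87 | 79.6% |
| 10 | 140/80 = 1.75 | 77.0% |
| 15 | 140/85 = 1.65 | 74.5% |

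**6. Smaller SD in score-1 subjects, e = 0, all 97.** The pooled SD is √((82 × 2.9² + 15 × s²)/97).
- s = 1.0: pooled SD 2.70, power 87.1%.
- s = 2.0: pooled SD 2.78, power 85.0%.

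**7. Which comparison changes what.**

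| Comparison | Base population | Per-protocol criteria |
|---|---|---|
| PPS as written v primary mITT | changes | change |
| PPS as written v ITT analysis (6.6.1.2.2) | same | change |
| ITT analysis v primary mITT | changes | same |
| Per-protocol subjects within mITT v primary mITT | same | change |

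The last row is the one the SAP does not provide. The second row is like for like only if linearity holds. If it fails, 6.6.1.2.7.5 moves to ANCOVA, while the ITT analysis follows the primary to MMRM.

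**The case against.** **The adherence question can be answered elsewhere.** The ITT sensitivity analysis covers all randomised subjects with the same event handling and, when linearity holds, the same model. Per-protocol against ITT is the customary comparison, and ITT against mITT shows what the entry-score restriction does. This stands, and it limits the point to per-protocol against primary. It does not supply a per-protocol check of the primary result itself. The entry-score subgroups in SAP 6.6.4 are not specified within the per-protocol set. The on-treatment analysis does use the mITT, but SAP 5.3.1.2 admits on-study assessments or those within 4 weeks of the last infusion, which read literally removes no on-study data.

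**The definition is defensible.** Score-1 subjects could meet the protocol's eligibility criteria, and the protocol's primary population is all randomised. A per-protocol set that does not inherit the later mITT restriction has some value. This also stands. Simply replacing the base population would lose the ITT counterpart, so both versions should be run.

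**The size is assumed.** Correct. The 0.84 is a natural-history decline, not a treatment effect. The 2.0 was set when the ITT population was primary and then carried over to 82 subjects.

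**Stronger readings that the documents do not support.** A reader might infer that the per-protocol estimate must look weaker even with perfect adherence. That follows only if the effect is smaller in score-1 subjects, and the documents do not give that effect. A reader might also infer that score-1 subjects cannot benefit. SAP 7 says only that there is no meaningful opportunity to demonstrate benefit, and it reports a decline that is not zero.

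**Conclusion.** The mismatch is plain in the text and nothing else in the SAP repairs it. The per-protocol analysis differs from the primary in both adherence and entry-score mix, so a gap between them has no single explanation.

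The size is an illustration: a shrinkage of about 9% to 15% (to 1.82 or 1.69). It rests on a 2.0-point mITT effect, a 15.5% share of score-1 subjects in the per-protocol set, and a score-1 effect between 0 and 0.84. At SD 2.9 throughout, power falls by about 6 points at zero effect with all 97 qualifying and by about 8 points in the 70-plus-15 case. The loss is under 1 point if score-1 subjects gain about 0.84, or if they gain nothing but have an SD near 1.0.

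This is a minor point of interpretation. The analysis is a sensitivity analysis outside the testing sequence in SAP Table 1, so the primary test, alpha and power are unaffected. If score-1 subjects do have a smaller effect in the same direction, the dilution runs towards no difference and would not manufacture support for the drug.

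**What to change.** In SAP 5.2.3 and 6.6.1.2.7, specify two per-protocol analyses:

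1. **Check of the primary result:** mITT subjects who meet the listed dose, assessment, completion and deviation criteria, compared with the primary mITT analysis.
2. **Counterpart of the ITT analysis:** the all-randomised set as now defined, labelled as such and compared with 6.6.1.2.2.

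The cost is one extra model run and a slightly smaller per-protocol set for the first analysis (at most about 82 subjects). No new data are needed. The change belongs in an SAP amendment before database lock and unblinding. If that point has passed, the first analysis can be reported in the CSR as an addition made after SAP sign-off.
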